In 2018 I did a chart review of 180 cases of low back pain in which I tested those who did not have lumbar pain using the SIFFT^x. I treated them with the appropriate exercise depending on the direction of the sacroiliac rotation. From this review, I found 16 cases of pain coming from the lumbar spine (9%). Of the remaining 164 given the appropriate 2 minute exercises, 78% found pain relief of which two thirds left the office entirely pain free. At that time, I also prescribed a pelvic support belt as, generally, a malrotated pelvis is an unstable pelvis^{xi}. As soon as the pelvis becomes malrotated again, the pain recurs. As the corrective exercise and pelvic support belt are two different treatments, the current research project will study them first separately for one month, then on follow-up after they have been used together for one month.

The aim of this study is to determine whether the pain relief and improved back function is temporary or if it can be reproduced and sustained by the patient at home, as needed with these two treatments. In order to test the effectiveness of each treatment alone and when they are combined, two sub-studies will be carried out as follows:

The first study is a superiority trial with a delayed control.

Population: ambulatory people between the ages of 19 and 90 suffering from low back pain, not of lumbar spine or hip origin, for at least three months.

Intervention 1 : teaching participants how to detect pelvic malrotation using the SIFFT then prescribing a two-minute exercise to correct pelvic malrotation, depending on its direction.

Intervention 2: prescribing a pelvic support belt to stabilize the pelvis.

Control: waiting list for one month, using usual treatments such as medications, alcohol and other drugs, chiropractic and other manipulation and physical therapy.

Outcome: a clinically significant change in Brief Pain Inventory (BPI) NRS pain score or in Oswestry disability Index (ODI) for low back pain.

Time: outcomes measured at baseline and after one month of using the assigned treatment at home.

The second study is a one month follow-up of the combined treatments.

Population: all previous study participants

Intervention: teaching all participants how to detect pelvic malrotation using the SIFFT then a two-minute exercise to correct pelvic malrotation depending on its direction followed by prescription of a pelvic support belt.

Control: BPI NRS pain severity score and ODI at one month assessment

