1.2. Hypotheses

The first study aims to find out if the recently developed exercises or the use of a pelvic support belt provide more than short term pain relief in the doctor's office:

Primary Hypotheses for the first study:

1. At 1 month, there will be significantly greater improvement in the ODI for low back pain score: at least 10% greater in those who are in treatment group 1 and are immediately taught how to perform the SIFFT followed by the appropriate exercise when compared to those on the waiting list for one month prior to being treated.
2. At 1 month, there will be significantly greater improvement in the ODI for low back pain score: at least 10% greater in those who are in treatment group 2 and are immediately given the pelvic support belt when compared to those on the waiting list for one month prior to being treated.

Secondary Hypotheses for the first study:

- 1 At 1 month, there will be significantly greater improvement in the BPI NRS pain severity score in those who are in treatment group 1 and are immediately taught how to perform the SIFFT followed by the appropriate exercise when compared to those on the waiting list for one month prior to being treated.
- 2 At 1 month, there will be significantly greater improvement in the BPI NRS pain severity score in those who are in treatment group 2 and are immediately fitted with a pelvic belt when compared to those on the waiting list for one month prior to being treated.

The follow-up study aims to find out if the recently developed exercises together with the use of a pelvic support belt provided more pain relief than each individual treatment:

Primary Hypothesis for the follow-up study:

- 1 At 2 months, there will be significantly greater improvement in the ODI for low back pain score compared to their one-month score in all participants.

Secondary Hypothesis for the follow-up study:

- 1 At 2 months, there will be significantly greater improvement in the BPI NRS pain severity score compared to their one-month score in all participants.

2.0 Recruitment:

Participants making a first appointment at the clinic for back pain will be in contact with my medical office assistant, [name], and invited to participate in this study. If they would like to participate, she will send them the consent form and eligibility questionnaire. If they are eligible, she will schedule them for their first visit.

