2.2 Sample Size

This study will recruit 20 participants per treatment group (60 participants overall). This sample size will allow the researchers to pilot this design.

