3.2.1 Sacroiliac Forward Flexion Test (SIFFT)

Everyone of the “idiopathic” low back pain participants is asked to stand, with their belt undone, leaning on one of the office counters with their legs vertical and their body, flexed at the hips, horizontal (Figure 1). This causes the innominate bones to be tilted forward with the horizontal body and lifted-up by the vertical legs while the weight of the torso brings down the spine and the sacrum. In this position, the PSISs (posterior superior iliac spines) face the examiner and are easier to palpate. The examiners then run their hands down the iliac crests to

Figure

locate the PSISs. Once these are located, they press down below the PSISs with the ulnar side of their thumbs abutting against the PSISs. They then ask the participants whether and on which side they feel pain. The pain may be due to pressure on the overstrained long dorsal sacroiliac ligaments which stabilize this joint. This is called the sacroiliac forward flexion test (SIFFT).

1: sacroiliac forward flexion test (SIFFT)

- Using a surgical marker, the examiner marks the area between his/her thumb and the PSIS on each side and writes the letter B (for before) on the painful side, on both sides if they have pain on both sides. He/she then asks the participant to stand and places a horizontal level on the lowest mark (Figure 2). He/she then measures the distance between the level and the highest mark in centimetres (Figure 3).

Figure 2: using a level on the lowest PSIS

[figure not shown]
[figure not shown]

Figure 3: measuring the distance between levels

The marks indicate the direction and extent of the malrotation:

- if the PSIS on the painful side is higher than that on the asymptomatic side, there is an anterior malrotation of the painful side ileum on the sacrum.
- If it is lower, there is a posterior malrotation of the painful side ileum on the sacrum.

The physician will record the degree of malalignment and its direction. If the participant is part of group 3 they are given a return appointment to be treated with both the exercises and the pelvic support belt one month later.

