3.5.1 Lost to Follow up Procedure

- When a participant is lost to follow-up, the last data collected will be entered in the database for each missed subsequent visit.

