5.0 Statistics

5.1 Outcome Measures

5.1.1A Primary Outcomes For the First Study

- difference in the change in ODI score in the initial treatment visit questionnaire and at the assessment visit one month later in the control group compared to the change from the treatment visit questionnaire to the 1 month assessment follow-up visit in the immediate SIFFT and exercise treatment group.
- difference in the change in ODI score in the treatment visit questionnaire and at the assessment visit, one month later, in the control group compared to the change from the treatment visit questionnaire to the 1 month assessment follow-up visit in the immediate pelvic support belt treatment group.

5.1.2A Secondary Outcomes For the First Study

- difference in the change in BPI NRS pain severity scores in the treatment visit questionnaire and at the assessment visit, one month later, in the control group compared to the change from the treatment visit questionnaire to the 1 month follow-up assessment visit in the immediate SIFFT and exercise treatment group.
- difference in the change in BPI NRS pain severity scores in the treatment visit questionnaire and at the assessment visit, one month later, in the control group compared to the change from the treatment visit questionnaire to the 1 month follow-up assessment visit in the immediate pelvic support belt treatment group.

5.1.1B Primary Outcome For the Follow-up Study

- difference in the change in ODI score in the assessment visit questionnaire and at the reassessment visit, two months later, for all groups.

5.1.2B Secondary Outcome For the Follow-up Study

- difference in the change in BPI NRS pain severity scores in the assessment visit questionnaire and at the reassessment visit, two months later, for all groups.

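### The follow-up test pools the waiting-list group, so it can be significant when exercise plus belt adds nothing to either treatment alone

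*Combined protocol and SAP*

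**What the plan says.** Section 1.2 gives the follow-up study a comparative aim: whether exercise and belt together "provided more pain relief than each individual treatment". The primary hypothesis under that aim is "greater improvement in the ODI for low back pain score compared to their one-month score in all participants" at 2 months. The secondary hypothesis says the same for the BPI pain score.

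Section 1.1 takes everyone from the first study as the population of the second and sets its comparator as "Control: BPI NRS pain severity score and ODI at one month assessment". Section 5.1.1B defines the primary outcome as "difference in the change in ODI score in the assessment visit questionnaire and at the reassessment visit, two months later, for all groups". Section 5.2 plans one Student t-test for ODI and one for BPI over the month of combined use. It does not say whether the test is paired, and it does not split it by group.

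By the month 1 visit the groups have had different things. Group 1 has used the exercises and group 2 the belt. Group 3 has been on a "waiting list for one month, using usual treatments such as medications" and other non-study care. Section 3.2.1 says that in "group 3 they are given a return appointment to be treated with both the exercises and the pelvic support belt one month later", and section 3.3 confirms that group 3 starts both at that visit.

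**The concern.** The aim is about added benefit over a single treatment. Only groups 1 and 2 have a single-treatment score at month 1. Group 3's month 1 score is a usual-care score, so its change to month 2 carries no information on that aim, yet it supplies a third of the sample.

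Pooling also cannot answer for each treatment. A gain from adding exercise to the belt can hide the fact that adding the belt to exercise does nothing.

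At stake is the follow-up study's primary conclusion. A significant pooled result, read against the stated aim, would be reported as the combination beating either treatment alone. It could come entirely from group 3 starting treatment, or from only one of the two treatments working. The error grows with success in the first study: the better a single treatment works, the more likely the wrong conclusion.

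**Working it through.** **Inputs from the plan.** 20 per group, 3 × 20 = 60 in all (section 2.2); two-sided 5% level (section 5.2); a hypothesised advantage over waiting of at least 10% on the ODI (section 1.2); last value carried forward after loss to follow-up (section 3.5.1).

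**Assumptions.** The plan gives no SD of change, so 10, 12, 15 and 20 ODI points are used. Its 10% is read as 10 ODI points, with 5 and 15 as alternatives. The t-test is taken as paired (one-sample on the month 1 to 2 change). Changes are normal, with 40,000 simulated trials per setting. Only results in the direction of benefit are counted, so the nominal rate is 2.5%.

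**Step 1: the shift.** Let the true improvement from month 1 to month 2 be 0 in groups 1 and 2 (the second treatment adds nothing) and D in group 3. The pooled mean is (20×0 + 20×0 + 20×D)/60 = D/3. For D = 10 it is 3.3 points, whatever the SD.

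**Step 2: a hand check for D = 10.** The test sees a variance of SD² + D² × (1/3)(2/3) = SD² + 22.2. At SD 10 its standard error is √(122.2/60) = 1.43, and significance needs a mean above 2.00 × 1.43 = 2.86. The mean itself varies with standard error 10/√60 = 1.29. The chance is about Φ((3.33 − 2.86)/1.29) = Φ(0.37) = 64%.

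**Step 3: simulated chance of a significant benefit.**

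| True change in groups 1, 2, 3 | Participants tested | SD 10 | SD 12 | SD 15 | SD 20 |
|---|---|---|---|---|---|
| 0, 0, 5 | 60 | 23% | 17% | 13% | 9% |
| 0, 0, 10 | 60 | 64% | 50% | 36% | 23% |
| 0, 0, 15 | 60 | 92% | 81% | 64% | 43% |
| 0, 0, 10, with 20% carried forward | 60 | 53% | 41% | 29% | 19% |
| 0, 10, 10 | 60 | 99.8% | 98% | 91% | 70% |
| 0, 10 (groups 1 and 2 only) | 40 | 81% | 67% | 50% | 32% |

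In the first four rows the combination adds nothing to either treatment. In the last two, exercise is worth 10 points and the belt nothing: the combination does beat the belt, but not exercise, so a claim about each treatment would be false. Dropping group 3 therefore removes the first problem but not the second.

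**Step 4: group 1 tested alone when the belt adds nothing.** The rate is the nominal 2.5%. This holds only if there is no time trend and no continuing benefit of the exercises. A 3-point trend raises it to 25%, 19%, 13% and 9% at the four SDs.

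**Step 5: an unpaired t-test instead.** With D = 10 and an assumed correlation of 0.6 between months, the rates are 34%, 21%, 11%, 6% and 5% at cross-sectional SDs of 10, 12, 15, 18 and 20. They are smaller, but all above 2.5%.

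**The case against.** Pooling is inferred. Section 5.2 does not say how the t-test is formed, and the outcome in section 5.1.1B, defined for all groups, could mean one result per group. That is a possible reading, but the hypothesis itself refers to all participants and no per-group test is planned. If a per-group result was meant, the text needs the same correction.

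Section 1.1 can also be read as making the second study simply a month of follow-up on the combined treatments, in which case including group 3 is deliberate and only the aim sentence in section 1.2 is out of place. This has some force. But section 1.2 attaches a primary hypothesis to a comparative aim, so the result will be read against it.

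Section 5.2 also plans descriptive statistics at each time point and covariate-adjusted group comparisons of change from baseline. If reported by group, these would show group 3's late improvement. They do not repair the test: by month 2 every group has had the combination, and no arm stays on a single treatment.

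Three qualifications stand. The rates depend on the assumed SD, and most of them on pairing. The case where the second treatment adds nothing at all is a boundary case. And the remedy is itself an uncontrolled before-after comparison.

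**Conclusion.** The concern holds. As worded, the follow-up hypothesis does not test the follow-up aim. The D/3 shift follows from the design and needs no outside figure: it is present whenever group 3 improves on starting treatment, which is what the first study hopes to show. How often it produces a false claim depends on assumptions. With a 10-point gain in group 3, a paired test and an SD of change between 10 and 20, it is about 64% down to 23%; with a 5-point gain, 23% down to 9%. The same fault applies to the BPI hypothesis. It should be fixed, because it concerns the follow-up study's primary hypothesis and the error runs towards a false positive.

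**What to change.** In sections 1.2, 5.1.1B, 5.1.2B and 5.2, replace the all-participant test with two paired comparisons of month 2 with month 1, for ODI and likewise for BPI:

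- group 1: belt added to exercise;
- group 2: exercise added to belt.

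Give each its estimate and 95% CI. Do not pool them for the claim about each treatment, and make that claim only if both comparisons show it. Report group 3's change separately, as its first month of combined treatment after usual care. State that these are within-participant changes with no concurrent single-treatment control, so a time trend or continuing benefit of the first treatment cannot be excluded. If an all-participant summary is kept, label it a description of the month of combined use and do not cite it for the aim. Rewording the aim to that description alone would also remove the contradiction, but would give up the question.

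**Cost.** Only wording changes; no new data. Precision falls because each comparison uses 20 participants instead of 60: the standard error rises by √(60/20) = 1.73, about 73%.

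| | SD 10 | SD 12 | SD 15 | SD 20 |
|---|---|---|---|---|
| 95% CI half-width, n = 60 (ODI points) | 2.6 | 3.1 | 3.9 | 5.2 |
| 95% CI half-width, n = 20 (ODI points) | 4.7 | 5.6 | 7.0 | 9.4 |
| Power, one group, 10-point added gain | 99% | 94% | 81% | 57% |
| Power, both groups, 10-point added gain | 98% | 89% | 65% | 32% |
| Power, one group, 5-point added gain | 57% | 42% | 30% | 18% |
| Power, both groups, 5-point added gain | 32% | 18% | 9% | 3% |

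The half-width is t(0.975, n − 1) × SD/√n. The both-groups rows are the square of the one-group power, since the groups are independent. Power for the joint claim is low unless the added gain is large or the SD small. Section 2.2 says "This sample size will allow the researchers to pilot this design", so estimates with wide intervals are in keeping with the study's size; the report should say that a joint claim may be out of reach.

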2.1 Randomization and group assignment

. After a potential participant has been examined, determined to be eligible and consents to participate they will be randomly assigned to treatment group 1, 2 or 3 according to the randomization scheme developed using “research randomizer”. Group 1 for immediately teaching the participant the SIFFT and appropriate exercises, group 2 for fitting of the pelvic support belt and group 3 for delayed treatment.

2.2 Sample Size

This study will recruit 20 participants per treatment group (60 participants overall). This sample size will allow the researchers to pilot this design.

2.3 Inclusion Criteria

- Age 19 to 90 Participants present with pain in their low back (below the waist) or their buttock.
- Able to attend all 3 study visits at the participating physician’s office (assessment visit, exercise and pelvic belt visit and one- month follow-up visit)
- Able to attend the first two visits with someone willing to assist them in assessing their back and help them with the necessary exercise if need be.
- Willing to perform the corrective exercise at home as needed
- Their PSISs are not level on initial examination.

- The long dorsal sacroiliac ligament below at least one of the PSISs is tender to palpation on initial examination.

2.4 Exclusion Criteria

- Pain experienced is lumbar in origin
- Pain secondary to hip or other pathology
- PSISs are level at initial examination
- No tenderness to pressure under the PSISs
- Severe pain elsewhere in the body, making the assessment of back pain difficult.
- Presence of ankylosing spondylitis (seen on x-ray, pain worse at night, relieved by exercise, abnormal CRP or ESR)
- Obvious leg length discrepancy ($> 1 \frac{1}{2}$ cm) when measured umbilicus to medial malleolus.
- Location of PSISs cannot be assessed accurately due to back mice or obesity.

3.0: Procedures

3.1 Prior to First Treatment Appointment

On first contacting the office, people with low back pain will be told about the research project. If they wish to participate, they will be sent a consent form, together with a questionnaire to determine their suitability for the study, by mail or email. They will be told about the www.low-back-pain.info website and given an appointment. They will be told that, preferably, they should be accompanied at this visit by someone able to help them with their back pain.

3.2 Randomization and First Treatment Visit

- Prospective participants presenting with pain in their low back (below the waist) will be given a questionnaire about medications, alcohol and marijuana as well as the other therapies they currently use for pain relief. They will be given the BPI NRS pain severity questionnaire and ODI questionnaire .
- To rule out lumbar origin pain, physical examination will include straight leg raise, knee and ankle reflexes, Babinski, and tests for sensitivity to touch, pinprick and vibration below the knee. If these tests indicate lumbar origin pain, they will be eliminated from the study and replaced by another participant, but their number and data will be retained.
- Range of motion of the hips will then be tested and those with painful limitation of hip range of motion will also be eliminated and their data entered into the study.
- All participants will be tested for hypermobility using the Beighton score as, in the chart review, 15% of those with sacroiliac joint sprains were also hypermobile.

- The active straight leg raising test will be carried out to assess sacroiliac dysfunction^{xv}.
- Obvious leg length discrepancy (greater than 1½ cm) will be assessed as this causes scoliosis and sacroiliac strain as well as making it impossible to test the PSISs levels. The shorter leg will be prescribed a heel lift, participants will be sent for x-ray evaluation of leg length and excluded from the study.
- The lower back and buttocks will be examined for back mice or excess fat, making the exact location of the PSISs difficult to assess. If this is the case participants will be excluded but their data will be entered in the database.
- As gluteus medius and minimus as well as the piriformis muscle are major stabilizers, iliopsoas, biceps femoris and quadratus lumborum are secondary stabilizers of the sacroiliac joints, these may develop a compensatory overuse tendinosis in response to the sacroiliac malrotation, we will check for tenderness to palpation where these muscles insert on the ilium, the greater and lesser trochanter, the ischium, the head of the fibula and the edge of the sacrum.

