5.2 Statistical Analysis

Data will be analyzed using PASW Statistics 18, Release 18.0.0, IBM. Analysis will be performed by intention-to-treat. Descriptive statistics (mean value \pm standard deviation (SD)) will be calculated for outcome variables at each time point. Baseline between-group data will be analyzed for significant differences by t-tests for nominal variables and Pearson chi square tests for categorical variables. Baseline characteristics will be included in the model as covariates for those variables with a significant between group difference. Analyses of covariates will be applied to compare the groups for magnitude of change in the 0-10 NRS pain score and Oswestry Disability Index between baseline and each follow-up time point (0, 1 and 2 months). A two-tailed P value $<.05$ will be used as the statistical significance level.

- a Pearson's chi-square-test will be done to assess the significance of the difference in Oswestry low back disability score over a 1 month period between

those who are treated with the immediate SIFFT and exercise treatment group, the immediate pelvic support belt group and those who are in the observation group.

- A second Pearson's chi-square will be done to assess the significance of the difference in BPI NRS pain severity score over a 1 month period between those who are treated with the immediate SIFFT and exercise treatment group, the immediate pelvic support belt group and those who are in the observation group.
- A student t-test will be done to assess the significance of the difference in ODI score over a one month period when both treatments are used simultaneously.
- A student t-test will be done to assess the significance of the difference in BPI NRS pain severity score over a one month period when both treatments are used simultaneously.
- The average and standard deviation for all the other data will be calculated and reported on.

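### No allocation concealment is described for a trial whose examining physician judges partly subjective eligibility and then treats, and the replacement wording in section 3.2 leaves unclear whether anyone can be removed after assignment

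*Combined protocol and SAP*

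**What the plan says.** On timing, section 2.1 is explicit: "After a potential participant has been examined, determined to be eligible and consents to participate they will be randomly assigned" to one of three groups. The list comes from a scheme made with Research Randomizer. The section does not say who keeps the list, who reads off the next assignment, or whether the examiner can see it.

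Section 3.2 carries randomisation in its heading and lists the examinations, but has no step at which assignment is made. For the lumbar check, "physical examination will include straight leg raise, knee and ankle reflexes, Babinski, and tests for sensitivity to touch, pinprick and vibration below the knee". Where the findings point to a lumbar origin, people are to be treated as follows: "they will be eliminated from the study and replaced by another participant, but their number and data will be retained". The later bullets on hip movement, leg length and PSIS location also remove people, but mention neither a replacement nor a number.

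Section 3.2.1 describes the sacroiliac forward flexion test (SIFFT), has the physician record the malalignment, and continues directly: "If the participant is part of group 3 they are given a return appointment".

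Several criteria in sections 2.3 and 2.4 depend on the examiner's hand or judgement. They include tenderness of the long dorsal ligament, PSISs that are not level (no minimum difference is given), and "Location of PSISs cannot be assessed accurately due to back mice or obesity". Section 5.2 states: "Analysis will be performed by intention-to-treat".

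**The concern.** Randomisation protects the comparison only if the person deciding who enters cannot know or guess the next arm. Here the examiner who palpates, marks and measures in section 3.2.1 appears, from section 3.2.2, to be the one who delivers the corrective exercise. Section 1.1 adds that the author of the protocol developed the test. If that person can see the list, borderline people can be kept or excluded according to the arm they would get, and the groups then differ before treatment starts. Intention-to-treat does not repair this, because anyone excluded on that basis never enters the analysis set.

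The wording in section 3.2 adds to the problem. Elimination, replacement and a retained number are terms that fit someone who already holds a place in the trial. A site that numbered people from the allocation list on arrival would either use up an assignment with each elimination or hand the replacement an arm that is already known.

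**Working it through.** **1. The plan's own figures.** Section 2.2 gives 20 per group in three groups: 3 × 20 = 60, as stated. The chart review in section 1.1 gives 16 lumbar cases among 180: 16/180 = 8.9%, stated as 9%. Section 2.2 gives no effect size, SD or power, so there is no sample-size formula to test. The point concerns procedure and does not rest on these figures.

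**2. What the retained number could mean.**
- *Screening identifier.* Section 3.2 opens by calling those examined prospective participants. Those eliminated were then never randomised. This agrees with sections 2.1 and 5.2.
- *A count.* Section 4.1 lists the number of people presenting with back pain as a data item. This also agrees with sections 2.1 and 5.2.
- *A place on the allocation list.* People would then be removed after assignment, against section 2.1 and against the intention-to-treat analysis in section 5.2.

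No sentence assigns a number before the examination or ties a number to an arm, so the text does not settle which is meant.

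**3. Does the concealment gap depend on that choice?** No. Suppose section 2.1 is followed exactly. The eligibility decision is made just before the assignment is looked up, and nothing prevents the examiner from having seen the next entry on an open list.

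**4. How many people the lumbar rule might touch.** At the chart-review rate, 60/(164/180) = 65.9, so about 66 are examined and about 6 eliminated. This is not a floor, because section 3.1 sends trial attenders a suitability questionnaire first. It bears on allocation only under the third reading.

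**5. Illustrative size, removal from one arm only.** The fractions 5% and 10% are assumptions. If the examiner removes exactly the worst-outcome fraction f, the mean of those remaining shifts by φ(z)/(1 − f) SD, where z is the normal cut-off for f:
- f = 5%: φ(1.645)/0.95 = 0.1031/0.95 = 0.109 SD
- f = 10%: φ(1.282)/0.90 = 0.1754/0.90 = 0.195 SD

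This is a ceiling, since it assumes perfect prediction. If the examiner's impression correlates r with outcome, multiply by r:
- r = 0.3: 0.033 to 0.058 SD
- r = 0.5: 0.054 to 0.097 SD

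That gives about 0.03 to 0.10 SD. The documents give no Oswestry Disability Index (ODI) SD. For an assumed SD of 10 to 20 points, the ceiling is 1.1 to 3.9 points, and the imperfect-prediction range is 0.3 to 2.0 points.

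**6. Illustrative size, removal from both arms.** A simulation with no true effect removed 2 of 22 in each of two arms, in opposite directions, leaving 20 against 20. The removals and r are assumptions. The test was a two-sided 5% t-test.

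| r | False difference (SD) | Type I error |
|---|---|---|
| 0.3 | 0.10 | 6.4% |
| 0.5 | 0.17 | 8.7% |
| 1.0 | 0.34 | 25% |

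With no arm-dependent removal, the error stayed at about 5%.

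**The case against.** The strongest reply is that the plan already has the right order. Section 2.1 could hardly be clearer on timing, and section 3.2 speaks of prospective participants. Group membership first appears in the visit sequence at the end of section 3.2.1, after the lumbar, hip, leg-length and PSIS checks. That order is what section 2.1 requires. On this view those eliminated were never randomised, and their absence from the intention-to-treat set is correct. This stands. A reader might infer from section 3.2 that people are numbered from the list first and that the two sections contradict each other. The documents do not support that; they support an ambiguity.

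A reader might also infer that people are replaced on subjective findings. Only the lumbar bullet mentions replacement, and its neurological tests are less open to judgement than palpation. The more subjective criteria sit in sections 2.3 and 2.4 and in the PSIS bullet, which carry no replacement rule. Part of the screening also happens before the visit, through the questionnaire and the office assistant (sections 2.0 and 3.1).

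Finally, this is a 60-person pilot, and sealed envelopes are only one way to conceal. Both points are fair. Neither removes the gap, because section 5.2 plans significance tests and a pilot of this design is also a trial of its allocation procedure. No argument on this side identifies a holder of the list or a concealed release.

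**Conclusion.** Two things hold. First, the plan describes no allocation concealment, although eligibility rests partly on palpation and judgement by someone who apparently also treats. This holds even if section 2.1 is obeyed to the letter. Second, the retained-number wording in section 3.2 must be reconciled with sections 2.1 and 5.2, because one of its possible meanings is removal after assignment.

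Two further inferences go beyond the documents. Knowledge of the arm during the eligibility decision is possible but not shown. Loss of the planned 20 per group would follow only if the retained number were a place on the list and the replacement did not take the vacated arm.

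The SD shifts and error rates show what an open list could do under stated assumptions. They do not estimate bias in this trial, and the upper ends require perfect prediction of outcome. The change is worth making because the analysis cannot repair lost concealment.

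**What to change.** - **Section 3.2:** define the retained number as a screening number given before randomisation and kept for people who are excluded.
- **End of section 3.2.1, before the group instructions:** add a step that assigns the next randomisation number only after the section 2.3 and 2.4 criteria, the SIFFT measurement and the baseline ODI and Brief Pain Inventory are recorded.
- **Section 2.1:** state that the medical office assistant, who already handles enrolment, holds the list and releases each assignment from sequentially numbered, opaque, sealed envelopes or by an equivalent concealed method.
- **Sections 2.1 and 5.2:** state that nobody is eliminated or replaced after assignment and that everyone randomised stays in the intention-to-treat set.

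The cost is a few sentences, 60 envelopes if that method is used, and about a minute per visit. No new staff are needed.
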